***Safety Follow-up Period***

After completion of study treatment, subjects will continue to be monitored on the study for 6 weeks and will have a phone call to assess safety at Weeks 49 and 51 and will return for the Safety Follow-up Visit (Week 54).

For subjects with early termination, end of study procedures (Week 48) will be performed, and subjects will be encouraged to return to the clinic for the Safety Follow-up Visit after 6 weeks. Phone calls will be performed to assess safety at Week 1 and Week 3 after end of study procedures are performed.

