
 
1. Visit 10/ET MRI will be done only in subjects who had a screening MRI performed and may be done up to 8 days prior to Visit 10/ET. CT scans of the brain can be used instead of MRIs, only in subjects who have an absolute contraindication for MRI.
 
2. Administer the first MMSE as early in the screening period as possible. MMSE score should be <math>\geq 12</math> and <math>\leq 24</math> at both screening and Visit 2, and a <math>\leq 3</math>-point difference between visits, for inclusion in the study.
 
3. Oral biomarker samples include subgingival plaque and buccal cell swabs (only at selected sites).
 
4. Subjects will have follow-up oral examinations at 24 and 48 weeks.
 
5. Visit 10/ET oral examinations may be completed up to 8 days prior to Visit 10 (or ET) when applicable.
 
6. Baseline (V2) LP must be done after the baseline MMSE score has been verified and subject's eligibility has been confirmed, and prior to the first dose of study drug. To allow flexibility of scheduling the LP procedure, the MMSE and then the LP may be performed up to 7 days prior to baseline V2. Likewise, the LP at Visit10/ET may be performed up to 7 days prior to the other visit procedures, even if the LP is outside the visit window. The LP procedures must be
 
																				

- performed as per SOC and site specific SOPs, if applicable (including imaging before and/or during the LP, if required).
7. A pre-dose trough sample will be drawn at all visits 2, 3, and 7 immediately prior to the AM dose, and the subject will then take their dose of study drug on-site. The exact times of AM dosing and PK sample collections at the site will be documented. A single post-dose sample will be drawn from each subject while on-site at the clinic per the following schedule: V2 30 minutes - 4 hours; V3 60 minutes ± 30 minutes; V7 2 hours ± 30 minutes; V9 3 hours ± 30 minutes; and V10/ET 4 hours ± 30 minutes.
  8. At visits when the subject takes their dose of study drug on-site, ECGs should be measured approximately 1-1.5 hours after dosing.
  9. At Visit 3 and Visit 7, ECGs will also be performed at trough (prior to dosing).

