### **7.10 Study Treatment: Visit 10/Early Termination (Day 336 ± 8)**

Note: To accommodate the logistics of performing the LP procedure, it may be done up to 7 days prior to V10/Day 336. Please make every effort possible to have the visit scheduled in the morning so the AM dose can be taken in the morning. Ideally, daily doses should be taken 12 hours apart and no less than 6 hours apart.

The following evaluations will be performed at this visit or at Early Termination in the following order as close as possible when feasible:

1. Administer last dose of double-blind study drug at the site;
2. Blood/urine sample collection:
  - a. Safety laboratory tests;
  - b. PK - A single post-dose sample will be drawn from each subject while on-site at the clinic at 4 hours ± 30 minutes post-dose. The exact times of AM dosing and PK sample collections at the site will be documented.
  - c. Serum and whole blood (PBMCs) for biomarkers;
  - d. Pregnancy test (only if urine pregnancy test is positive);
3. Adverse events;
4. Oral examination and collection of oral biomarker samples (SGP and buccal cell swabs) at selected sites (will be completed within 8 days before Visit 10 [or Early Termination] when applicable).
5. 12-lead ECG 1-1.5 hours post-dose
6. MRI of the brain, only in subjects who had a screening MRI performed, and has to be done within 8 days prior to Visit 10. CT scans of the brain can be used instead of MRIs, only in subjects who have an absolute contraindication for MRI;
7. ADAS-Cog 11;
8. MMSE;
9. ADCS-ADL;
10. CDR-SB;
11. NPI;
12. Winterlight Speech Assessment (only in English speaking (primary language subjects and only in the US and UK);
13. Concomitant medications;
14. Symptom-based physical examination;
15. Saliva collection;

16. Weight;
  17. Vital signs;
  18. Lumbar puncture to collect CSF;
  19. Urine pregnancy test (women of child bearing potential only);
  20. C-SSRS;
  21. Informed consent will be obtained for subjects who agree to participate in the open label extension portion of the study; and
  22. Inclusion/exclusion will be evaluated to determine eligibility for subjects who want to participate in the open label extension portion of the study.  
Dispense OLE study drug – subjects who participate in OLE only. The subject should be instructed to take the first dose of COR388 in the morning of the next day.
- NOTE:** Effective 16 February 2021, the OLE portion of the study was terminated by the Sponsor.

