### **8.21 Blood Pharmacokinetic (PK) Evaluations**

At Visit 2 a pre-dose trough sample will be drawn immediately prior to the AM dose. The subject will take their first dose at the site with the dose time and date recorded in the eCRF. A PK blood draw will be collected within the first 4 hours after the dose (at any time between 30 minutes to 4 hours post-dose).

At Visit 3, Visit 7, Visit 9, and Visit 10 (or Early Termination), subjects will return to the clinic prior to taking their AM dose. A pre-dose trough sample will be drawn at Visit 3 and Visit 7 immediately prior to the AM dose. The subjects will then take their dose of study drug on-site and the exact time of the dose ingestion will be recorded. A single post-dose sample will be drawn from each subject while on-site at the clinic at 60 minutes  $\pm$  30 minutes, and at 2 hours  $\pm$  30 minutes, respectively.

At Visit 9 and Visit 10 single post dose sample will be drawn from each subject while on-site at the clinic at 3 hours  $\pm$  30 min and at 4 hours  $\pm$  30 min, respectively. The exact time of the last dose of study drug will be recorded.

In all cases, the exact clock time of each PK sample will be recorded.

Plasma samples will be quantified for COR388 (and potential metabolites of interest). Data will be analyzed by a population pharmacokinetic approach to derive COR388 (and potential metabolites of interest) systemic exposure metrics. A

detailed population PK analysis plan will be generated and finalized prior to the PK analysis being initiated.

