## 8.23 Electrocardiograms (ECGs)

Standard 12-lead electrocardiograms (ECGs) will be performed at Screening (Visit 1), Visit 2, Visit 3, Visit 4, Visit 5, Visit 7, Visit 9, Visit 10 (or Early Termination), and Visit 11 (Safety Follow-up Visit). The Investigator will review ECGs for any changes from baseline. At Visit 2, Visit 3, Visit 7, Visit 9, and Visit 10 (or Early Termination), subjects will take their dose on-site and the exact time of the dose ingestion will be recorded. The time to maximum plasma concentration of COR388 ( $T_{max}$ ) is approximately 1-1.5 hours. At visits when the subject takes their dose of study drug on-site, ECGs should be measured approximately 1-1.5 hours after dosing. At Visit 3 and Visit 7, ECGs will also be performed at trough (prior to dosing). ECGs will be reviewed by a cardiologist at the central ECG laboratory to identify any abnormalities and verify automatically calculated values of RR, PR, QRS, and QTc intervals. Clinically significant ECG events and abnormalities will be recorded as adverse events.

Open Label Extension: Standard 12-lead ECGs will be performed at Visits OLE-1, OLE-2, OLE-4, OLE-6 (or Early Termination) and OLE-9 (OLE Safety Follow-Up Visit). **NOTE:** Effective 16 February 2021, the OLE portion of the study was terminated by the Sponsor.

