### **12.13 Removal of Subjects from Therapy or Assessment**

Liver Safety Monitoring (laboratory analyte testing) must be performed at each study visit within the prespecified visit window (see [Table 1](#) and [Table 2](#), Schedule of Evaluations) OR the study drug dosing must be temporarily halted until the testing is done.

Subjects who discontinue IP dosing for IP-related safety reasons will not be permitted to resume IP treatment and must be followed until the safety concern (e.g. transaminase elevations) or an existing AE has stabilized or resolved/returned to baseline. At that time subject's participation in the study must be terminated early and V10/ET procedures must be performed. Subjects should remain in the study through final 6-weeks safety follow up period which ends with a final study visit.

A subject will be considered to have completed the study when he or she completes Visit 11. If a subject is discontinued at any time after randomization into the study, the Investigator will make every effort to follow the subject and complete the Visit 10/Early Termination assessments.

A termination electronic case report form (eCRF) page should be completed for every subject who receives investigational product, whether or not the subject completes the study. The reason for any early discontinuation should be indicated on this form. The primary reason for a subject discontinuing early should be selected from the following standard categories of early termination:

- *Adverse Event (Adverse Reaction)*: Clinical or laboratory events occurred that, in the medical judgment of the Investigator for the best interest of the subject, are grounds for discontinuation. This includes serious and nonserious adverse events (AEs) regardless of relation to the investigational product.
- *Death*: The subject died.
- *Withdrawal of Consent*: The subject desired to withdraw from further participation in the study in the absence of an Investigator-determined medical need to withdraw. If the subject gave a reason for withdrawing, it should be recorded in the eCRF.

- *Protocol Violation*: The subject's findings or conduct failed to meet the protocol entry criteria or failed to adhere to the protocol requirements (e.g., drug noncompliance, failure to return for defined number of visits). The violation necessitated early discontinuation from the study.
- *Lost to Follow-Up*: The subject stopped coming for visits and study personnel were unable to contact the subject.

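### The Visit 10/Early Termination checklist gives an on-site dose with no condition, although subjects stopped for drug-related safety are sent to that visit and barred from resuming drug

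*Protocol*

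**What the plan says.** **The dose at Early Termination.** Section 7.10 states that its list applies at Visit 10 or at Early Termination. Item 1 is "Administer last dose of double-blind study drug at the site". Item 2b then takes a PK sample 4 hours after the dose, and item 5 an ECG 1 to 1.5 hours after it. Section 8.23 says that at "Visit 9, and Visit 10 (or Early Termination), subjects will take their dose on-site". Section 8.21 says that at "Visit 10 (or Early Termination), subjects will return to the clinic prior to taking their AM dose", and then that the dose is taken on-site. Table 1 note 7 lists a post-dose sample at "V10/ET 4 hours ± 30 minutes".

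**Who attends.** The Synopsis (Safety Follow-up Period) says: "For subjects with early termination, end of study procedures (Week 48) will be performed". Section 12.13 deals specifically with drug-related safety stops. These subjects are followed until the problem has stabilized or resolved; their participation "must be terminated early and V10/ET procedures must be performed".

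**The bar on drug.** The same paragraph of Section 12.13 begins: "Subjects who discontinue IP dosing for IP-related safety reasons will not be permitted to resume IP treatment". Section 9.1.5 describes re-challenge as restarting dosing after an interruption and disallows it after a drug-related safety stop, naming liver-injury cases as an example. Section 8.24 lists liver findings after which rechallenge should not be attempted.

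**The concern.** Two instructions meet in the same subject at the same visit. One says give a dose; the other says this subject may not have drug again. A coordinator working down the Section 7.10 list would give a capsule to someone in whom the drug had been stopped for a reason judged related to it.

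The order of the list adds to this. The dose is item 1, ahead of the safety laboratory sample (2a), the adverse event review (3), the physical examination (14) and vital signs (17). Section 12.13 also accepts a problem that has merely stabilized, so the subject need not have returned to baseline. Liver safety is an active issue in this trial: the DMC's recommendation after its November 2020 meeting led to more frequent liver testing.

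The stake is subject safety and clear instructions to sites. No endpoint, sample size or error rate is involved.

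**Working it through.** The plan states no figure to reproduce; the check is a comparison of the sections.

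1. **Does the list apply to stopped subjects?** Yes. Section 7.10 covers Early Termination by name, and Section 12.13 makes the V10/ET procedures mandatory after a drug-related safety stop.

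2. **Is the dose item conditional?** No. Other items in the list carry conditions: the MRI is done "only in subjects who had a screening MRI performed", the pregnancy test applies to women of child-bearing potential, and the speech assessment applies to certain English speakers. The allowance for feasibility in the lead-in concerns the order of procedures and exempts nobody from the dose.

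3. **Do other sections supply the missing condition?** No.
   - Section 8.23 names Early Termination among the on-site dosing visits.
   - Section 8.21 does the same, less directly.
   - Table 1 note 7 states on-site dosing only for Visits 2, 3 and 7. For V10/ET it gives the timing of a post-dose sample, so it presupposes a dose without ordering one.
   - Table 1 note 8 makes the ECG timing depend on an on-site dose but does not say who is exempt from that dose.

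4. **Would the dose count as re-challenge?** Yes. Under Section 9.1.5, any restart after an interruption qualifies, so one capsule is enough.

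5. **Does the liver rule reach every liver stop?** Section 8.24 gives four stopping criteria for ALT or AST, set here against its no-rechallenge list:

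| Stopping criterion | No-rechallenge entry that covers it |
|---|---|
| above 8x ULN | above 5x ULN |
| above 5x ULN for over 2 weeks | above 5x ULN |
| above 3x ULN with raised bilirubin or INR | same criterion |
| above 3x ULN with symptoms, rash or eosinophilia | same criterion |

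   All 4 of 4 are covered, so every subject stopped under these criteria is also in the group that should not be rechallenged.

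6. **What would detect harm after the dose?** Hepatic or gastrointestinal symptoms, or an AST/ALT elevation, trigger testing under Section 8.24, and a value above 2x ULN triggers weekly testing. The Synopsis and Section 7.11 provide structured calls, 1 and 3 weeks after Early Termination. These calls include no blood test. The next scheduled laboratory test is at Visit 11, 6 weeks later. A silent enzyme rise that began after a normal sample at Early Termination would not be looked for until then.

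**The case against.** The strongest reply is that the protocol already resolves the matter. Section 12.13 puts the bar and the V10/ET instruction in one paragraph, so read together they mean the visit without drug. The Synopsis also says that subjects continue on drug unless the investigator stops it for safety or tolerability. The phrases about a last dose and a morning dose suit someone still on treatment. Section 8.5 does not list Visit 10 as a double-blind dispensing visit.

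Much of this stands as a forecast of conduct: a careful site would probably withhold the dose. It does not stand as a reading of the text. Nothing gives Section 12.13 precedence over the visit list, and none of these phrases exempts a stopped subject from an instruction that Sections 7.10 and 8.23 give flatly for Early Termination.

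A reader might infer three stronger things that the documents do not support:

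- **That Table 1 note 7 is a further order to dose.** It only times a sample. The instruction rests on Sections 7.10, 8.21 and 8.23, and 8.21 is the least direct of these.
- **That a site withholding the dose commits a protocol deviation.** That assumes Section 7.10 outranks the safety bar. Such a site is obeying Sections 12.13 and 9.1.5.
- **That the protocol intends re-challenge, or that subjects were re-dosed.** The bars in Sections 12.13 and 9.1.5 show the opposite intent, and the protocol says nothing about what sites did.

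**Conclusion.** The conflict is real and is in the current text. Followed as written, the Early Termination checklist directs a dose that Sections 12.13 and 9.1.5 forbid and that Section 8.24 says should not be attempted after a liver stop.

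The size is modest. Exposure is one capsule per affected subject: 40 mg, 80 mg or placebo, so active in two of three arms. The protocol gives no rate of drug-related safety stops, so the number of subjects at risk cannot be derived. The trigger-based testing and the two calls reduce the harm without closing the 6-week gap in scheduled laboratory tests.

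The conclusion assumes only that a site may work from the visit list as printed. It is a wording error with a safety consequence and should be corrected. It has no bearing on the efficacy analysis.

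**What to change.** 1. **Section 7.10 item 1.** Keep "Administer last dose of double-blind study drug at the site" and add in parentheses: at Early Termination, only if the subject is still taking study drug; do not dose a subject whose study drug has been stopped.

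2. **Section 7.10 items 2b and 5, Sections 8.21 and 8.23, and Table 1 notes 7 and 8.** State that a subject already off study drug at Early Termination has one untimed ECG and no post-dose PK sample. Alternatively, take an untimed PK sample and record the date and time of the last dose.

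The cost is one clause and matching wording at the next amendment. One dose-timed PK sample and one dose-timed ECG are lost in each subject already off drug; after a drug-related safety stop, those data could be had only by giving the prohibited dose. Sample size, endpoints and alpha are unchanged.

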#### **7.11 Safety Follow-up Phone Calls: (Days 343 ± 2 and 357 ± 2)**

Adverse events and any changes to concomitant medications will be evaluated during these phone calls. The follow-up phone calls will be structured and scripted to ensure completeness and standardization. The general structure of the inquiry will be open ended inquiry about any new symptoms, specific questioning about any reported sign or symptom and then a structured questioning about neurologic and withdrawal sign and symptoms by body system as seen with benzodiazepines and opiates and amphetamines. These will be conducted after either Visit 10 or Early Termination.

**NOTE:** Subjects who choose to participate in the open label extension portion of the study will not complete the safety follow-up phone calls and continue with the Schedule of Evaluations in [Table 2](#).

**NOTE:** Effective 16 February 2021, the OLE portion of the study was terminated by the Sponsor.

#### **7.12 Safety Follow-up Visit: Visit 11 (Day 378 ± 8)**

After completion of study treatment, subjects will continue to be monitored on the study for 6 weeks and will return for the Safety Follow-up Visit (Week 54).

For subjects with early termination, end of study procedures (Week 48) will be performed, and subjects will be encouraged to return to the clinic for the Safety Follow-up Visit after 6 weeks.

**NOTE:** Subjects who choose to participate in the open label extension portion of the study will not complete the safety follow-up visit and continue with the Schedule of Evaluations in [Table 2](#).

**NOTE:** Effective 16 February 2021, the OLE portion of the study was terminated by the Sponsor.

The following evaluations will be performed at this visit in the following order or as close as possible when feasible:

1. ADAS-Cog 11;
2. MMSE;
3. ADCS-ADL;
4. CDR-SB;
5. Concomitant medications;
6. Saliva collection;
7. Symptom-based physical examination;
8. Vital signs;
9. C-SSRS;
10. Blood/urine sample collection:
  - a. Safety laboratory tests
11. 12-lead ECG; and
12. Adverse events.

### **7.13 Increased Safety Laboratory Monitoring (Liver Safety Monitoring)**

Per DMC recommendation (following the November 16, 2020 meeting) the following increased laboratory analyte testing is being implemented:

- Every 2 weeks for the initial 12 weeks
- Every 3 weeks as of Week 12 through Week 24
- Every 4 weeks as of Week 24 through Week 32

Liver Safety Monitoring (laboratory analyte testing) must be performed at each study visit within the prespecified visit window (see [Table 1](#), Schedule of Evaluations) OR the study drug dosing must be interrupted until the testing is done.

#### **7.14 Open Label Extension (OLE)**

**NOTE:** Effective 16 February 2021, the OLE portion of the study was terminated by the Sponsor.

Subjects who complete Visit 10 may be eligible to participate in the open label extension portion of the study. If subjects meet inclusion and none of the exclusion criteria, and sign the informed consent, they will continue in the open label extension portion and not complete the Safety Follow-up Phone Calls or the Safety Follow-up Visit: Visit 11 (Day 378  $\pm$  8). Laboratory testing and ECG results from Visit 9 will be used to evaluate eligibility.

Subjects who are not eligible or do not consent to the open label extension will proceed to the Safety Follow-up Phone Calls (Days 343  $\pm$  2 and 357  $\pm$  2) and the Safety Follow-up Visit: Visit 11 (Day 378  $\pm$  8).

#### **7.15 OLE Study Treatment: Visit OLE-1 (Day 350 $\pm$ 3)**

The following evaluations will be performed at this visit in the following order or as close as possible when feasible:

1. Concomitant medications;
2. Symptom-based physical examination;
3. Vital signs;
4. C-SSRS;
5. 12-lead ECG;
6. Blood/urine sample collection:
  - a. Safety laboratory tests;
7. Adverse events; and
8. Dispense study drug.

#### **7.16 OLE Study Treatment: Visit OLE-2 (Day 378 $\pm$ 3)**

The following evaluations will be performed at this visit in the following order or as close as possible when feasible:

1. Concomitant medications;
2. Symptom-based physical examination;
3. Vital signs;
4. C-SSRS;
5. 12-lead ECG;
6. Blood sample collection:
  - a. Safety laboratory tests;
7. Adverse events; and
8. Dispense study drug.

### **7.17 OLE Study Treatment: Visit OLE-3 (Day 420 ± 3)**

The following evaluations will be performed at this visit in the following order or as close as possible when feasible:

1. ADAS-Cog 11;
2. ADCS-ADL;
3. CDR-SB;
4. Concomitant medications;
5. Symptom-based physical examination;
6. Vital signs;
7. C-SSRS;
8. Blood/urine sample collection:
  - a. Safety laboratory tests;
9. Adverse events; and
10. Dispense study drug.

### **7.18 OLE Study Treatment: Visit OLE-4 (Day 504 ± 3)**

The following evaluations will be performed at this visit in the following order or as close as possible when feasible:

1. ADAS-Cog 11;
2. ADCS-ADL;
3. CDR-SB;
4. Concomitant medications;
5. Saliva collection;
6. Symptom-based physical examination;
7. Vital signs;
8. C-SSRS;
9. 12-lead ECG;
10. Blood sample collection:
  - a. Safety laboratory tests;
11. Adverse events; and
12. Dispense study drug.

### **7.19 OLE Study Treatment: Visit OLE-5 (Day 588 ± 6)**

The following evaluations will be performed at this visit in the following order or as close as possible when feasible:

1. Concomitant medications;
2. Symptom-based physical examination;
3. Vital signs;
4. C-SSRS;
5. Blood/urine sample collection:
  - a. Safety laboratory tests;

6. Adverse events; and
7. Dispense study drug.

